## PROTOCOL SYNOPSIS

Study Title	Vibratory Stimuli: A Novel Rehabilitation Method for Preventing Post-Traumatic Knee Osteoarthritis
Funder	US Department of Defense
Clinical Phase	Phase II
Study Rationale	
Anterior cruciate ligament injury and reconstruction surgery (ACLR) dramatically increase the risk of developing knee osteoarthritis (OA). Individuals with ACLR possess deficits in quadriceps muscle function and proprioception (joint position sense) that alter knee joint loading during tasks such as walking in manners that contribute to development of knee OA. Vibratory stimuli enhance quadriceps function and proprioception and may, therefore, reduce the risk of knee OA. The purposes of this study are to 1) evaluate and compare the effects of whole body vibration (WBV) and local muscle vibration (LMV) on quadriceps function, knee joint proprioception, and walking gait biomechanics in individuals with ACLR and 2) identify characteristics that determine the efficacy of WBV and LMV for improving quadriceps function, knee joint proprioception, and walking gait biomechanics in individuals with ACLR.

Study Objective(s)	
Primary
 
 
• To determine the effects of WBV and LMV on quadriceps function, proprioception, and gait biomechanics in individuals ACLR
 
• To compare the effects of WBV and LMV on quadriceps function, proprioception, and gait biomechanics in individuals ACLR
 
• To identify factors that predict the effects of LMV and WBV on quadriceps function, proprioception, and gait biomechanics in individuals ACLR
 

Test Article(s)	WBV or LMV delivered at a frequency of 30Hz and intensity of 2g
Study Design	
This preclinical investigation will utilize a single-blind randomized controlled experimental design whereby 75 individuals with primary unilateral ACLR will be randomly assigned to WBV, LMV, and Control groups. Stratified randomization into 3 groups of equal size (<math>n = 25</math>) will be performed using a computer generated randomization algorithm to ensure stratification with respect to age and time since ACLR.

Subject Population	Inclusion Criteria
key criteria for Inclusion and Exclusion:	
 
1. Subjects age 18-35
 

---

2. Undergone primary unilateral ACLR within 6 months to 5 years of participation

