## 1.3 Non-Clinical and Clinical Study Findings

Quadriceps strengthening is an inherent component of rehabilitation of ACLR and other traumatic knee injuries, but is commonly ineffective due to the fact that the underlying neural deficiencies (i.e. AMI) are not addressed by conventional approaches. However, both direct (local muscle vibration - LMV) and indirect (whole body vibration - WBV) vibratory stimuli enhance quadriceps function in individuals with non-pathological knees, and may minimize the negative effects of AMI. We demonstrated that LMV enhances quadriceps function in healthy individuals, and that both WBV and LMV produce

equivalent improvements in quadriceps function following experimental knee joint effusion (i.e. simulated knee trauma) in healthy individuals. Vibratory stimuli also improve proprioception, and we demonstrated that improving knee proprioception decreases impulsive loading during walking gait in individuals diagnosed with knee OA. *These findings suggest that vibratory stimuli may improve quadriceps function, proprioception, and gait biomechanics (e.g. impulsive loading) following traumatic knee injuries, potentially reducing the risk of developing knee OA.*

Our preliminary data and findings reported by other researchers support our hypothesis that vibratory stimuli may enhance rehabilitation of traumatic knee injuries. These studies indicate that incorporation of vibratory stimuli into ACLR rehabilitation improves postural stability, quadriceps strength, and proprioception. Additionally, a recent animal model demonstrated that WBV minimized articular cartilage loss in rats with knee OA caused by ACL transection. However, *the effects of vibratory stimuli on factors linked to the development of post-traumatic knee OA have yet to be investigated.*

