2. **WBV and LMV enhance quadriceps function similarly in individuals with simulated knee trauma.** We evaluated the effects of WBV and LMV on quadriceps function in healthy individuals with simulated knee trauma (n=43). The underlying cause of quadriceps dysfunction, AMI, is attributable to sensory information that signals pathology including pain, inflammation, swelling, and damage to mechanoreceptors. AMI can also be induced experimentally by injecting saline into the knee joint which mimics the effects of swelling/effusion. Quadriceps function was assessed via the central activation ratio (CAR). CAR quantifies an individual’s ability to voluntarily activate a muscle, and is an indicator of AMI. A detailed description of this method is provided in the RESEARCH STRATEGY below. Following pre-test measures, 60mL of saline was injected into the knee joint space to induce AMI. Subjects were then exposed to WBV, LMV, or no vibration (Control), and quadriceps function was reassessed post-intervention. The interventions and methods for assessing quadriceps function utilized in this preliminary study are identical to those proposed in the RESEARCH STRATEGY. CAR improved significantly with WBV (+8.3%) and LMV (+5.9%), but not in the Control group (+0.7%). While both forms of vibration improved quadriceps function, this improvement did not differ between LMV and WBV. Additionally, subjects who experienced the greatest inhibitory effects of effusion displayed the greatest improvements in quadriceps function with vibratory stimuli. *These findings support our hypothesis that WBV and LMV may enhance quadriceps function similarly in individuals with knee pathology.* We

anticipate that individuals with “real” knee pathologies (as opposed to the acute, simulated trauma in this preliminary investigation) will realize substantially larger improvements in quadriceps function due to the chronic nature of their quadriceps dysfunction.

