### **6.3 Sample Size and Power**

Quadriceps function is the primary outcome for this investigation, as it is the critical factor in controlling impulsive knee joint loading linked to development of post-traumatic knee OA. We conducted *a priori* power analyses using data from our preliminary investigation involving these same vibratory stimuli following experimental knee joint effusion. Pre-post change scores were calculated as described above in the statistical methods for Specific Aim 1, and effect size indices were calculated for one-way ANCOVA using pre-test scores as the covariate. These analyses indicate that a sample of 45-63 subjects (15-21 per group) would provide statistical power of 0.80 for  $\alpha = 0.05$  to identify significant overall ANCOVA models for CAR ( $f = 0.48$ ) and peak torque ( $f = 0.41$ ), where  $f$  is the effect size calculated as the square root of the ratio of the between-group sum of squares and the error sum of squares. Further, these preliminary data generated the pairwise effect sizes presented in the table below calculated using the following equation:

$$\text{Effect Size} = \frac{[\Delta\text{WBV} \text{ (or } \Delta\text{LMV} \text{ )} - \Delta\text{Control}]}{\text{Pooled Standard Deviation}}$$

Effect Sizes for *Post Hoc* Group Comparisons of Pre-Post Change Scores

Quadriceps Function Variable	WBV vs. Control	LMV vs. Control	LMV vs. WBV
CAR	0.84	0.78	0.36
Peak Torque	0.98	0.70	0.35

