Statistical power for the effect sizes given in Table 2 was calculated for one-tailed independent t-tests. These estimates indicate that a sample of 39-78 subjects (13-26 per group) would provide statistical power of 0.80 for  $\alpha = 0.05$  to evaluate pairwise comparisons between the Control group and each vibratory intervention (i.e. Aim 1). In contrast, 194 subjects (97 per group) would be necessary to provide adequate power to identify the relatively small effect sizes for comparing the two vibratory interventions (i.e. Aim 2). The associated mean differences in CAR between WBV and Control and between LMV and Control were 8.26% and 5.86%, respectively, while the difference between LMV and WBV was only 0.68%. Similarly, the associated mean differences in peak torque between WBV and Control and between LMV and Control were 0.29 N/kg and 0.20 N/kg respectively, while the difference between LMV and WBV was only 0.04 N/kg. These data suggest that the small mean differences in the dependent variables between WBV and LMV, even when powered sufficiently, are not likely clinically or physiologically relevant. Therefore, we will recruit a sample of 75 individuals (25 per group) to address the proposed specific aims. This sample size will provide adequate power to demonstrate similar improvements in quadriceps function with WBV and LMV.

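### Section 6.3 gives WBV–LMV differences that contradict its own differences from Control, and claims power to show similarity that a difference test with 25 per group does not have

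*Combined protocol and SAP*

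**What the plan says.** The Synopsis lists among the primary objectives: "To compare the effects of WBV and LMV on quadriceps function, proprioception, and gait biomechanics in individuals ACLR". Section 6.3 states "Quadriceps function is the primary outcome for this investigation", so WBV against LMV on quadriceps function is a primary comparison.

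Section 6.3 then makes four statements about that comparison:

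- The pilot effect sizes for LMV against WBV are 0.36 (CAR) and 0.35 (peak torque), and 97 per group would be needed to detect effects of that order.
- The CAR differences from Control were 8.26% (WBV) and 5.86% (LMV), "while the difference between LMV and WBV was only 0.68" percent. For peak torque they were 0.29 and 0.20 N/kg, "while the difference between LMV and WBV was only 0.04 N/kg".
- On that basis the differences between the two modalities, "even when powered sufficiently, are not likely clinically or physiologically relevant".
- The trial will therefore recruit 25 per group, and "This sample size will provide adequate power to demonstrate similar improvements in quadriceps function with WBV and LMV".

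Section 6.2 analyses Aim 2 with one contrast, WBV against LMV, on covariate-adjusted change scores at the two-sided 0.05 level. Neither section gives an equivalence margin, a confidence-interval criterion or a rule for interpreting a non-significant result.

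Section 1.4 (item 2) reports the pilot by group: "CAR improved significantly with WBV (+8.3%) and LMV (+5.9%), but not in the Control group (+0.7" percent). Section 1.3 summarises the same pilot as showing "equivalent improvements in quadriceps function following experimental knee joint effusion".

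**The concern.** Two differences from the same Control group fix the third by subtraction. The three figures that Section 6.3 gives for CAR do not satisfy this, and neither do the three for torque. The figures that fail are the ones used to argue that the gap between the modalities does not matter.

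The closing sentence is a separate problem. Section 6.3 first concedes that 25 per group is far too few to detect the pilot difference, then presents the same sample as adequate to show that the modalities are similar. Low power to detect a difference is not power to establish similarity. A non-significant result is the expected outcome even if the pilot difference is real, and nothing in Section 6.2 prevents it from being reported as similarity. The background already describes pilot gains of 8.3 and 5.9 points as equivalent. It also gives practical reasons to prefer LMV (portability, and a cost of about $250 against as much as $10,000 for WBV), so a null result could influence the choice of device.

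**Working it through.** **Inputs.** From Section 6.3: effect sizes for WBV–Control, LMV–Control and LMV–WBV of 0.84, 0.78, 0.36 (CAR) and 0.98, 0.70, 0.35 (torque); mean differences 8.26, 5.86, 0.68 CAR points and 0.29, 0.20, 0.04 N/kg; 25 per group; power 0.80. From Section 6.2: two-sided alpha 0.05 for Aim 2. From Section 1.4: CAR changes of +8.3, +5.9 and +0.7 for WBV, LMV and Control.

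**1. The plan's own figure.** A two-sample t-test (noncentral t) with d = 0.36, one-tailed 0.05 and power 0.80 needs 97 per group, as stated. The sample-size arithmetic is therefore not the fault. The two-sided test in Section 6.2 would need 123 per group.

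**2. Subtraction.**

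- CAR: 8.26 − 5.86 = 2.40 points (2.39 to 2.41 with rounding), against 0.68 stated. Ratio 2.40/0.68 = 3.5.
- Torque: 0.29 − 0.20 = 0.09 N/kg (0.08 to 0.10 with rounding), against 0.04 stated. Ratio 0.09/0.04 = 2.25.

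Covariate adjustment does not explain this, because contrasts of adjusted means from one model also subtract.

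**3. Cross-check through the effect-size table.** Implied pooled SD = difference / effect size.

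| Contrast | CAR, as stated | Torque, as stated |
|---|---|---|
| WBV–Control | 8.26/0.84 = 9.8 | 0.29/0.98 = 0.30 |
| LMV–Control | 5.86/0.78 = 7.5 | 0.20/0.70 = 0.29 |
| LMV–WBV | 0.68/0.36 = 1.9 | 0.04/0.35 = 0.11 |
| LMV–WBV by subtraction | 2.40/0.36 = 6.7 | 0.09/0.35 = 0.26 |

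The stated LMV–WBV differences do not fit their own effect sizes. The subtracted ones come close.

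**4. Probable source.** 8.26, 5.86 and 0.68 round to the within-group changes in Section 1.4 (+8.3, +5.9, +0.7), so 0.68 is very probably the Control group's change. The true differences from Control would then be 8.26 − 0.68 = 7.58 and 5.86 − 0.68 = 5.18, with implied SDs 7.58/0.84 = 9.0 and 5.18/0.78 = 6.6. The WBV–LMV gap is 2.40 points on either reading. This is inference: equal-sized groups with these pooled SDs would need group SDs of about 9.0 (WBV), 2.7 (LMV) and 9.0 (Control), and the overall f rebuilds to about 0.42, not the stated 0.48. For torque the documents give no within-group changes, so only the failure to subtract is certain.

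**5. What 25 per group can do for WBV against LMV.** Results are in SD units; the range reflects 48 df (two groups) or 71 df (three groups with one covariate).

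- Two-sided power at d = 0.36: 0.24.
- Power with the pre-test covariate, replacing d by 0.36/√(1 − r²): 0.26, 0.31 and 0.42 for r = 0.3, 0.5 and 0.7. These correlations are assumptions; the documents give none.
- True difference giving 50% power: 0.56 to 0.57 SD. Below that, non-significance is the likelier result.
- 95% confidence-interval half-width: t × √(2/25) = 1.994 × 0.283 = 0.56 SD (71 df) or 2.011 × 0.283 = 0.57 SD (48 df).
- Two one-sided tests at 0.05 each, with zero true difference, reach 0.80 power at a margin of about 0.84 SD.

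In CAR points, with SDs from 6.7 to 9.0 (the reading in step 4), the half-width is 3.8 to 5.1 and the margin 5.6 to 7.6. With the SD of 9.8 implied by the labels as printed, the upper ends become 5.6 and 8.3. On every reading the half-width exceeds the 2.40-point gap.

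**The case against.** The strongest reply is about weight. The figures 0.68 and 0.04 are pilot results in a narrative; they enter no model, hypothesis or sample-size formula, and 97 per group comes from the effect size. The plan also discloses that 75 subjects cannot detect the pilot difference, so power of 0.24 only quantifies an admitted limit. Both points are correct. Neither answers the defect, which is the additional claim of adequate power for similarity.

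The closing sentence can also be read as saying that each modality improves on Control by a similar amount. One-tailed power at 25 per group for those contrasts is 0.90 and 0.86 (CAR) and 0.96 and 0.79 (torque). But showing that each beats Control does not show that the two gains are alike, so this reading does not support the sentence either.

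Some of the objection stands. The documents give no minimum important difference, so 2.40 points or 0.09 N/kg might still be judged unimportant; what fails is the support offered, not necessarily the judgement. Which torque figure is wrong is unknown. The pilot SDs are unresolved, so conversions to CAR points are conditional. The description of the pilot as equivalent is background text, not a decision rule for this trial.

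**Conclusion.** The concern holds and should be corrected before the plan is relied on. The mean differences in Section 6.3 cannot all be right. If the Control contrasts stand, the WBV–LMV gap is 2.40 CAR points and about 0.09 N/kg; the CAR gap is the same if the three CAR figures are within-group changes. The argument that the gap is irrelevant therefore rests on inconsistent numbers.

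The stated power to demonstrate similar improvements is not a property of this design. There is no equivalence criterion to be powered for, and the margin that 25 per group could support (about 0.84 SD) is as large as the pilot's whole CAR effect of vibration over Control (0.78 to 0.84 SD). Figures in SD units assume equal groups of 25, normal errors and no covariate gain; only the adjusted powers also depend on assumed correlations.

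**What to change.** **Section 6.3**

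- Check the mean differences against the pilot data and restate them so that they subtract. Label any within-group changes as such.
- Remove the inference of irrelevance drawn from 0.68 and 0.04. If the judgement is kept, justify it against the reconciled differences.
- Delete the sentence claiming adequate power to demonstrate similar improvements. State instead that Aim 2 is an estimation aim, with 95% confidence limits of about ±0.56 SD before covariate adjustment.

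**Section 6.2, Aim 2**

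- Report the adjusted WBV–LMV difference with its 95% confidence interval.
- State that a non-significant result will not be interpreted as similarity.

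An equivalence margin is optional. If one is wanted, it needs its own justification and a matching sample size.

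The cost is a look-up of the pilot means and edits to two sections, with no change to the sample size or procedures. The plan gives up its promise of a similarity conclusion.

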## 7 STUDY INTERVENTION (drug, device or other intervention details)

### 7.1 Whole Body Vibration

Whole body vibration will be delivered in this investigation via a commercially available device (Power Plate pro5). This device oscillates in the vertical dimension at a frequency of 30 Hz and acceleration of 2g.

### 7.2 Local Muscle Vibration

The local muscle vibration stimulator to be used in this investigation is a custom-built prototype developed in collaboration with the Department of Industrial and Systems Engineering at North Carolina State University as part of a collaborative grant to be used explicitly for the purposes of the proposed study. As of 5/13/2015, this device has been used to enhance muscle function via the exact intervention proposed for this study in more than 100 subjects in multiple previously approved studies with no adverse events. Furthermore, 25 of these subjects had undergone ACL reconstruction surgery and met the inclusion criteria for the proposed investigation.

This stimulator consists of a single-axis electromagnetic oscillator mounted on a plastic frame. The plastic frame was produced via 3D printing such that its under surface is curved to accommodate the shape of the anterior thigh. The electromagnetic oscillator consists of a standard audio speaker that is coupled with a frequency generator through an amplifier that causes it to vibrate in the anterior-posterior direction (i.e. into the quadriceps muscle). This vibratory stimulus is similar to the mechanics of a reflex hammer when evaluating the tendon-tap/knee-jerk reflex clinically in that it creates rapid changes in quadriceps length, thus exciting the muscle via the muscle spindle system. Vibration frequency is held

constant at 30Hz as determined by the frequency generator in the controller unit, and the acceleration is constrained to 2g via feedback provided to the controller unit from an accelerometer mounted on the oscillator.

## **8 STUDY INTERVENTION ADMINISTRATION(if applicable)**

This preclinical investigation will utilize a single-blind randomized controlled experimental design whereby 75 individuals with primary unilateral ACLR will be randomly assigned to WBV, LMV, and Control groups. Stratified randomization into 3 groups of equal size (n = 25) will be performed using a computer generated randomization algorithm to ensure stratification with respect to age and time since ACLR. All individuals involved with data collection and analysis will be blinded to group allocation.

## **9 SAFETY MANAGEMENT**

### **Research Monitor Responsibilities and Authorities**

[name] from the UNC-Chapel Hill Department of Orthopaedics will serve as the Research Monitor for this investigation. [name] possesses both the research ethics and medical expertise necessary to carry out this role. The PI will provide the Research Monitor a summary report during each quarter of the funding period that details information necessary for him to perform the following responsibilities:

1. Enrollment data
  - a. # of subjects (total and per group)
    - i. The Research Monitor will be unblinded to group, but the PI and all research team members involved with data collection will remain blinded.
    - ii. Groups will be identified by number only (e.g. Group 1 = Control, etc.) in reports generated by the PI, and the Research Monitor will be provided a key to decode group membership by the unblinded research assistants who are delivering the interventions.
    - iii. The Research Monitor will evaluate enrollment data to ensure the enrollment rate is consistent with the project timeline (i.e. 30 subjects per year for Years 1 and 2; 15 for Year 3).
  - b. The Research Monitor will verify subjects meet the enrollment criteria
    - i. Relevant data regarding the inclusion/exclusion criteria (e.g. age, KOOS scores, CAR, time since ACL reconstruction surgery, etc.) will be entered in an electronic data management system (Epi Info, Centers of Disease Control and Prevention). This system is capable of generating spreadsheets for data organization. These spreadsheets will be provided to the Research Monitor to permit verification of the enrollment criteria.
2. Verify consent
  - a. Data entry in Epi Info will require the member of the research team who is entering a given subject's data to verify (yes/no) that written informed consent was obtained. This individual will also be required to enter his/her initials in Epi Info to confirm that consent was obtained. The Research Monitor will verify that each subject has been consented based on these data contained in the quarterly report.

### 3. Monitor adverse events

a. Subjects will be monitored for adverse events by the research team during data collection, and will be instructed to inform the research team immediately if they experience adverse events after leaving the laboratory. Information related to adverse events will be entered in Epi Info as described below.

#### i. Adverse Event? (yes/no)

1. If yes, was there appropriate follow up by research team?

a. Subjects will be contacted within 1 day of identification of an adverse event and again after 1 week. The dates of follow up by the research team will be documented in Epi Info.

2. Appropriate documentation sent to UNC-CH Biomedical IRB?

a. The dates of submission, IRB response, and resolution will be documented in Epi Info.

3. The Research Monitor will determine if the adverse event is associated with participation in the study using the UNC-CH Biomedical IRB decision tree

([http://research.unc.edu/files/2012/11/ccm3\\_018993.pdf](http://research.unc.edu/files/2012/11/ccm3_018993.pdf)). Documentation (e.g.

description of the adverse event, symptoms, etc.) will be sent to the Research Monitor for evaluation of risk which will be used to determine the following:

a. Severity of the adverse event as per US Department of Health and Human Services guidelines (<http://www.hhs.gov/ohrp/policy/addevntguid.html#AA>)?

b. Is this a recurring problem (i.e. multiple adverse events of the same type)?

c. Is this adverse event specific to one of the interventions?

